### **Measures**

(See appendix for measures) All assessments for this study will be completed on a laptop/tablet computer through web administration at in-person sessions held in women's primary care or dedicated research space at the VA in Waco and Temple.

**Overview of assessments:** Standard instruments will be administered to gather demographic data and to assess key constructs of ST, PTSD, IPV, alcohol use, as well as resource and treatment utilization. If other relevant constructs are identified in informant interviews, we will add measures to assess these constructs during the initial randomized control trial. Participants will complete screening assessments, and individuals randomized to the SHE intervention or SR

(control condition) will complete assessments at a 2- and 4-month follow-up. One of the two research assistants who is not involved in recruitment will be available during the assessments and masked to the intervention condition. If a participant is called for her medical appointment during her screening or assessments, the research assistant will offer to continue after her medical appointment or schedule a return visit.

All assessments are well established, with adequate reliability and validity, well-matched to our program components and aims. The baseline battery is designed to minimize assessment with the control group in order to take into account growing concerns regarding the motivational properties of assessment, leading to substantial Type II error in other MI-based intervention studies. The baseline assessment will occur immediately following the consent procedures, and will be self-administered on a laptop computer. Items from the screening and baseline assessments that will be used to generate the personalized feedback report (PFR) used in the intervention modules are marked with an asterisk (\*).

**Screening measures:** As described above, the screener will include the following brief series of questions about general health and the following well-validated, reliable and recommended measures. Lifetime ST will be assessed via the SES-SFV, items from the VA MST screener, as well as the CSVQ. Specifically, the SES-SFV will assess experiences of unwanted sexual contact, sexual coercion, attempted rape and rape experienced from the age of 14 to the time of the survey. The SES-SFV is commonly utilized in research of sexual trauma, and utilizes a series of 10 behaviorally-oriented and sexually-explicit questions to assess several types of victimization experiences. Prior research with the SES-SFV suggests that versions of the scale demonstrate good test-retest reliability ( $r = .93$ ), and adequately captures the legal definitions of attempted rape and rape. The quantity and frequency of alcohol use will be assessed during the screening using the Graduated Frequency Measure (GFM). An algorithm is utilized to quickly score the measure to determine whether the participant exceeds the national recommended limits for daily drinking (4 or more for women) over the specified recall period. Symptoms of PTSD will be assessed with PTSD Checklist for DSM-5 (PCL-5). Individuals will be classified as screening positive for current PTSD if the sum score is equal to or greater than 33. The PCL-5 is considered a “best practice” instrument in the assessment of PTSD. At screening, IPV in the past year will be assessed with the Woman Abuse Screening Tool (WAST), which was originally designed for use in primary care settings, is an 8-item instrument that measures physical, sexual, and emotional abuse in the last 12 months and is consistent with the definition of IPV as defined by The American College of Obstetricians and Gynecologists. It has correctly classified 100% of nonabused women and 92% of abused women in a known-group analysis, has good internal reliability, and has adequate concurrent validity. Consistent with similar studies, IPV status is positive if a woman obtains a score of 4 or more on the WAST.

**Baseline and follow-up measures of ST:** During the baseline assessment, further detail will be gleaned regarding the characteristics of ST experienced by study participants. A series of follow-up questions will be administered following the SES-SFV to ascertain characteristics of the assault, including the age at the time of the assault and whether the assault occurred during military service, (i.e., age 17 and younger, age 18 but before military service, during military service, after military service). The SES-SFV will also be administered at follow-up to assess for sexual victimization over the interim.

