### ***Subjects***

We will sample consecutive eligible patients from Women's Primary Care at the Waco and Temple VA medical centers. Participants will be women Veterans seeking treatment in women's primary care.. Participants must report a history of lifetime ST and have at least one of the following risks: 1) Alcohol (i.e., report exceeding the national recommended limits for daily drinking (4 or more for women) on at least one occasion in the past month); 2) PTSD (i.e., screen positive for current PTSD) and screen positive for IPV within the last 12 months. Participants who indicate one or more of these risk factors will be included in the study. Other inclusion criteria will be ability to understand study procedures in English, be between the ages of 18 and 65, and willingness to complete follow-up session. In future studies, the computer software can be modified to present information in Spanish for the Latina population.

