### ***Inclusion/ Exclusion Criteria***

#### **Inclusion Criteria**

-Female Veterans

-Lifetime history of ST with at least one risk factor: heavy drinking, screen positive for current PTSD or for IPV within last 12 months

-Age 18-65

-Seeking treatment through the Women's Primary Care Clinics at the Central Texas VA Healthcare System.

-Ability to understand study procedures in English

-Not actively in suicidal or homicidal crisis warranting imminent hospitalization

For this study, we will test the proposed intervention for English-speaking women Veterans only, because translation of the intervention and related assessments could not take place within the time constraints/demands of the current study. In future studies, the computer software can be modified to present information in Spanish for the Latina population. We specified the upper age limit because it reduces the likelihood of including women Veterans who have age-related brain diseases, which might confound our findings.

**Inclusion of Women** This proposal is primarily designed to investigate the efficacy of an intervention for women Veterans with ST. By definition, no adult men will participate in this study and adult women will be adequately represented. We will enroll women Veterans meeting inclusion criteria. Males will be excluded from participation because research has indicated a high prevalence of lifetime ST against women Veterans.

**Inclusion of Minorities** We expect that the representation of minorities in our sample will closely align to the demographics profile of women Veterans receiving care at CTVHCS. Specifically, American Indian/Alaska Native (.9%); Asian (1.4%); Black/African American (35.3%); Hispanic (9.4%); Native American/Other Pacific Islander (1.5%); White (45%).

**Inclusion of Children:** Children under the age of 18 will not be included. The target population is women Veterans, and the minimum age to serve in the military is 18.

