appointment at the women's clinic. If so, the participant will be provided with referrals, and screening will be postponed until their period of intoxication is over on the same day or rescheduled for a later date. To guarantee that the participant is not intoxicated prior at the time of screening, any participant who had either initially endorsed drinking alcohol prior to their rescheduled appointment and who did not endorse drinking alcohol on the day of their rescheduled appointment or participants who do not endorse drinking alcohol but exhibit behaviors consistent with intoxication (e.g., slurred speech, belligerence, etc...) will be administered a breath alcohol test, and must register  $<.02$  breath alcohol content. Once it is determined that the participant is not intoxicated, she will complete the 30-minute screener using the CIAS software delivered on a VA issued/ approved laptop computer or desktop computer to determine study eligibility. Participants will wear headphones to hear the audio for the computerized screening and a screen protector will be on the computer so no one could inadvertently observe the screen. The use of audio computer-assisted self-interview software to conduct screening will maximize identification rates of women Veterans with ST, IPV, alcohol misuse, and PTSD. The screener will include a brief series of questions about general health, exercise, diet, smoking, and sunscreen. The screener will also include the following well-validated, reliable and recommended measures: Participants must report a history of lifetime ST (as identified by the Sexual Experiences Survey—Short Form Victimization (SES-SFV), items from the VA MST screener, and the Childhood Sexual Victimization Questionnaire (CSVQ) and have at least one of the following risks: 1) Alcohol (i.e., report exceeding the national recommended limits for daily drinking (4 or more for women) on at least one occasion in the past three months as indicated on the Graduated Frequency Measure (GFM)); 2) PTSD (i.e., screen positive for current PTSD with a cut point of  $\geq 36$  on the PTSD Checklist for DSM-V; and IPV within the last 12 months (i.e., score 4 or more on the Woman Abuse Screening Tool (WAST)).

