**Table 1: Schedule of Assessment Measures**

Schedule of Assessments										
		Screening		Baseline		2-month		4-month		Measure Purpose
		SHE	Contro	SHE	Contro	SHE	Contro	SHE	Contro	
ST	SES-SFV+MST screener	X	X			X	X	X	X	Screening
	CSVQ	X	X							Screening
h c	GFM	X	X							Screening

	TLFB			X	X	X	X	X	X	Primary Outcome and Feedback
	RCQ			X	X	X	X	X	X	Attitude Change
	AUDIT			X	X	X	X	X	X	Exploratory Analyses
IPV	WAST	X	X							Screening
	CAS			X	X	X	X	X	X	Primary Outcome
	SPBC			X	X	X	X	X	X	Attitude Change
PTSD	THS			X	X	X	X	X	X	Primary Outcome
	PCL-5	X	X			X	X	X	X	Primary Outcome and Screening
Tx Use	EOR			X	X	X	X	X	X	Primary Outcome
	TSR			X	X	X	X	X	X	Primary Outcome
	ASPH			X	X	X	X	X	X	Attitude Change
Acceptability	SCSS			X						Treatment Acceptability
	CSQ-8			X						Treatment Acceptability
Relationship Function	QMI/ FAD-12			X	X	X	X	X	X	Secondary outcomes/covariate

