**Primary outcomes (Aim 4a):** Following the intention-to-treat principle, all women who completed the baseline assessment and who are randomized will be included in the analyses. Analyses will first test the hypothesis that SHE reduces the number of risks relative to control. Quantification of post-intervention behavioral change will be estimated by comparing the distributions of the number of risks in the two groups at baseline and follow-up. Within-person changes in the number of risks over time will also be examined. Specifically, women will be characterized by the number of risks (one through 3) at baseline. That will serve as a covariate in a model predicting number of risks at 2 and 4 months, which will be analyzed using generalized estimating equations (GEE) with a Poisson distribution specified. GEE is a method of repeated measures analysis commonly utilized for binary outcomes that allows for the inclusions of both categorical and continuous independent variables, as well as appropriate modeling of covariates when observations are correlated across time. The primary between group independent variable will be program group; dummy coded using the intervention as the reference category.

To further illustrate program effects, each of the participants will then be classified over the follow-up as 1) resolving all risks; 2) resolving some but not all risks; and 3) resolving no risks or increasing the number of risks. Intervention effectiveness will be measured by comparing the proportion of women resolving all risks, to the proportion of women resolving no risks or increasing risks between the groups. The proportion of women resolving all risks will also be compared to the proportion of women resolving some risks between groups.

**Secondary outcome (Aim 4b):** Analyses will also examine comparisons between groups in the extent of change in use of treatment (TSR and CPRS number of mental health visits) and resource utilization (EOR) (secondary outcome) as well as the extent of change on individual risk factors overtime using generalized estimating equations (GEE) (i.e., occurrence of IPV as measured by the CAS, screen positive for PTSD diagnosis as measured by the cut point of  $\geq 33$  on PCL-5, heavy drinking status as measured by the TLFB).

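### Two entry rules contradict themselves: the PCL-5 cut point (36 or 33) and the heavy-drinking look-back (one month or three)

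*Combined protocol and SAP*

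**What the plan says.** **PTSD cut point.** Section 3, Screening and Informed Consent Procedures, describes the computer screener that decides eligibility. A woman qualifies on PTSD if she is "screen positive for current PTSD with a cut point of" 36 or more on the PCL-5. Section 3, Measures (Screening measures), returns to the same screener, refers back to the earlier description, cites the same reference, and states: "Individuals will be classified as screening positive for current PTSD if the sum score is equal to or greater than 33". Section 4, Data Analysis (Secondary outcome, Aim 4b), defines the follow-up PTSD risk as "screen positive for PTSD diagnosis as measured by the cut point of" 33 or more. That is the only cut point the analysis text gives.

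**Heavy-drinking look-back.** Section 3, Subjects, requires exceeding the limit for "daily drinking (4 or more for women) on at least one occasion in the past month". Screening and Informed Consent Procedures requires the same thing "on at least one occasion in the past three months as indicated on the Graduated Frequency Measure (GFM".

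**Places that might have settled it.** The Inclusion Criteria list says only "heavy drinking, screen positive for current PTSD or for IPV within last 12 months", with no PCL-5 cut point and no drinking window. Measures says the Graduated Frequency Measure is scored "for daily drinking (4 or more for women) over the specified recall period" and does not name the period there.

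**The concern.** One risk is enough for entry, so each threshold can decide on its own whether a woman is in the trial. An eligibility rule must give one answer per woman, and here two of the three risk definitions do not.

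The same three risks make up the primary outcome, a count analysed with the baseline count as covariate. In the SHE arm, the risk profile also determines which modules a woman completes (Section 4, SHE Intervention). An unsettled threshold can therefore reach beyond enrolment, into what participants receive and how change is counted.

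**Working it through.** The plan states no figure on this point, so there is none to reproduce. The check is a comparison of the sections.

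| Rule | Section | Value |
|---|---|---|
| PCL-5, entry | Screening and Informed Consent Procedures | 36 or more |
| PCL-5, same screener | Measures, Screening measures | 33 or more |
| PCL-5, follow-up outcome | Data Analysis, Aim 4b | 33 or more |
| Heavy drinking, entry | Subjects | past month |
| Heavy drinking, entry | Screening and Informed Consent Procedures | past three months |
| Heavy drinking, primary analysis (TLFB) | Baseline and follow-up measures of alcohol use | past 30 days |
| Both | Inclusion Criteria | not given |

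The Aim 4b entry defines an outcome, not entry. It corroborates 33 as the analysis value, but the entry conflict on PTSD is between the screening section and Measures.

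**What follows without further assumption.** A PCL-5 score of 33, 34 or 35 as the only risk is eligible under Measures and ineligible under the screening section. Heavy drinking about 31 to 90 days ago as the only risk is eligible under the screening section and ineligible under Subjects.

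**What follows only under a condition.**

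1. In Table 1 the PCL-5 row, labelled "Primary Outcome and Screening", has entries at screening, 2 months and 4 months but none at baseline. The screening score must therefore supply baseline PTSD status. If it is classed at 36 and follow-up at 33, a woman who entered on another risk with an unchanged score of 33 to 35 appears to gain a risk. If the stored sum score is classed at one cut point throughout, no count is distorted.
2. The primary-outcome paragraph (Aim 4a) expects baseline counts of one to three but does not name the instruments behind them. If the three-month rule governs entry and baseline alcohol risk comes from the 30-day TLFB, a woman admitted on alcohol alone can have a baseline count of zero. The model can accept a zero covariate. She cannot, however, show the reduction defined in Power Analysis (one to none, two to one, three to two). If she stays at zero, she fits none of the three Aim 4a classes cleanly.

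**Size.** Taken one at a time, each conflict decides eligibility only for women with a single risk under the wider rule. Power Analysis projects 50 women with one risk. How many of them would hold it only under the wider rule is not given.

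An illustration for the PCL-5, which is not a bound: Power Analysis plans on 60% of included women screening positive, without naming a cut point. Assume normal scores with the SDs below, ignore selection at entry, and apply the 60% at 33 or more. Then mean = 32.5 + 0.2533 × SD, and the share scoring 33 to 35 = 0.60 − P(X > 35.5).

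| Assumed SD | Mean | Positive at 36 or more | Share at 33–35 | Of 155 |
|---|---|---|---|---|
| 20 | 37.6 | .541 | .059 | 9.1 |
| 15 | 36.3 | .521 | .079 | 12.2 |
| 12 | 35.5 | .501 | .099 | 15.3 |
| 10 | 35.0 | .481 | .119 | 18.4 |

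If the 60% is applied at 36 or more instead, mean = 35.5 + 0.2533 × SD. The shares are then .057, .075, .093 and .110 (8.8, 11.6, 14.4 and 17.0 of 155). All these counts include women with another risk, who are eligible under either cut point. Nothing in the documents supports an estimate for the drinking window.

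**The case against.** The strongest reply accepts both textual conflicts and disputes their weight.

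- **A computer applies the rule.** If one rule is programmed, every woman is treated alike and the harm is a misdescribed population, not case-by-case inconsistency. This is fair as to mechanism. But whichever rule is programmed, one section is breached systematically, and the text does not tell a reader which population was enrolled.
- **The unspecified recall period in Measures may point back to the three months in the screening section,** and the appendix of measures, which is not in the text reviewed, may state it. This stands, so the silence in Measures is not counted as a separate fault. It does not resolve Subjects against the screening section.
- **No section proposes 36 for the baseline count.** Correct, but the screening section classes that very score at 36, and it is the only PCL-5 score scheduled before follow-up. The risk has a basis in the text and remains conditional.
- **A zero baseline count can also arise because entry and baseline use different instruments.** This stands: reconciling the look-back alone would not remove it. It is also arguable that a woman who stays at zero falls literally into the class that resolved no risks. She would then be counted as a failure with nothing to resolve.
- **The illustrative counts rest on assumed SDs.** This stands, and the conclusion does not use them.
- **This is a developmental trial aimed at estimating an effect size.** That limits the inferential damage. It does not make two eligibility rules acceptable, since the estimate is meant to inform a larger trial in a defined population.

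**Conclusion.** The concern holds, with high confidence. Both contradictions stand in current text and neither is explained by redaction or extraction. Two of the three risk definitions that govern entry, and that also make up the primary outcome, have conflicting values. This must be corrected.

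The certain consequence is that eligibility is undetermined for women whose only risk is a PCL-5 score of 33 to 35, or heavy drinking within three months but not within one. The effects on the baseline count depend on how that count is built, which the plan does not say. The number of women affected is not computable from the documents. Because screening precedes randomization, both arms are affected alike and no between-arm bias is claimed. The documents do not establish which cut point or window was intended.

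**What to change.** 1. Reconcile Screening and Informed Consent Procedures, Measures and Data Analysis so that one PCL-5 cut point serves eligibility, module assignment, baseline count and outcome.
2. Reconcile Subjects and Screening and Informed Consent Procedures to one heavy-drinking look-back, and carry both values into the Inclusion Criteria list.
3. Check the programmed screener, including the scoring of the Graduated Frequency Measure, against the reconciled text.

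The choice of cut point and window is for the investigators.

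While the text is open, two smaller clarifications are worth making. Name the recall period of the Graduated Frequency Measure in Measures. In the Aim 4a paragraph, state which instrument and window supply each component of the baseline count and how a count of zero is handled. Entry uses the Graduated Frequency Measure and the WAST, whereas the baseline measures are the TLFB and the CAS, so a common look-back alone does not guarantee a baseline count of at least one.

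The cost is protocol wording and one check of the scoring algorithm, with no added participants or procedures.

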**Baseline and follow-up assessments of IPV:** : The Composite Abuse Scale (CAS) will assess the chronicity and occurrence of violence with their current partner (over the past year). At subsequent assessments it will be administered for the time since last assessment. The CAS, a widely used self-report of behaviors, has 30 items presented in a six point format requiring respondents to answer "never", "only once", "several times", "monthly", "weekly" or "daily"-over the specified time period. The CAS has 4 subscales that measure severe, combined abuse, emotional abuse, physical abuse, and harassment. The CAS has recently been published in the Centers for Disease Control and Prevention compendium of intimate partner violence measures. The scale will be coded categorically (no violence vs. any on one or more CAS subscales of combined abuse, emotional abuse, physical abuse, and harassment) for the primary study analyses. The scale will also permit exploratory analyses of decreasing the frequency of violence among participants.

The 15-item checklist the Safety-Promoting Behavior Checklist (SPBC) will be used to assess the participant's use of strategies that could protect her from IPV in the future (e.g., hiding money and extra clothing). All questions begin with the phrase, "Have you ever . . ." followed by specific safety-promoting behaviors. In subsequent assessments the same series of questions, it will be administered for the time since last assessment. The SPBC has been used successfully in interventions for women with IPV that have like SHE targeted an increase in safety behaviors.

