drinking), and/or reducing the number of negative consequences associated with drinking. Those participants that are currently not interested in or are ambivalent about changing their alcohol use will receive elements including pros/cons and normed feedback. Computer software can easily deliver such a bifurcated treatment approach – such an intervention design is consistent with evidence that motivational approaches may work best with less motivated individuals. For the IPV and PTSD modules, participants will indicate their readiness to utilize relevant resources (e.g., seek mental health for PTSD, remain in treatment, or re-engage in treatment, use IPV hotlines, talk to health care providers and/or support person about IPV/PTSD and IPV/PTSD resources), and the intervention will be tailored on the readiness of each participant. Consistent with MI, those reporting a goal of readiness to utilize resources will move more quickly to a section consistent with primary goal-setting which will include affirmations about utilizing resources, and encouraging the use of formal and informal social supports for maintenance of gains as well as self-care strategies; those who are not ready will receive elements including **pros/cons** and normed **feedback**.

At the end of each module, there will be video clips inserted of women Veterans with the particular risk factor, discussing ways in which they were able to reduce their risk, such as access care/resources, remain in treatment, and/or implement strategies to reduce the risk of IPV, and/or increase formal and informal support and self-care strategies. Each module will have a selection of videos that will be tailored to the woman Veteran’s profile. For instance, for women Veterans with PTSD who are in treatment, there will be a video clip of a women Veteran with PTSD discussing how treatment has helped her, and discussing ways in which she has increased her support system as well as self-care strategies. Participants will then have the option to create a personalized **Safety Plan**. Participants will select from a menu of potential personal change goals relevant to each risk module (e.g., reduce frequency or quantity of alcohol use; stop alcohol use; implement x% of a safety plan for IPV; implement complete safety plan) or optionally, can

enter their own change goals in free text. Participants will be provided with an optional one-page print-out of the Safety Plan as a resource.

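### As described, the CAS counts abuse by the current partner only, so former-partner abuse during follow-up can drop out of the IPV risk in the primary count

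*Combined protocol and SAP*

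**What the plan says.** All references are to the combined protocol and SAP.

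- **Scope of the IPV measure** (Section 3, Measures, baseline and follow-up assessments of IPV). The CAS "will assess the chronicity and occurrence of violence with their current partner (over the past year"). For later visits: "At subsequent assessments it will be administered for the time since last assessment". No wider partner definition is given there.
- **Coding** (same paragraph). For the primary analyses the scale is dichotomized as "no violence vs. any on one or more CAS subscales of combined abuse, emotional abuse, physical abuse, and harassment".
- **Role.** Table 1 marks the CAS as a primary outcome at baseline, 2 and 4 months in both arms. The secondary outcome text (Aim 4b) names only the CAS for occurrence of IPV.
- **Entry.** IPV eligibility is a WAST score of 4 or more, covering the last 12 months. No restriction to a current partner is stated, and the WAST is not repeated.
- **Use in the primary analysis** (Data Analysis, Aim 4a). The number of risks at 2 and 4 months is modelled by Poisson GEE with the baseline number as covariate. In addition, "each of the participants will then be classified over the follow-up as 1) resolving all risks", with two further classes for partial and no resolution.
- **The other victimization measure.** "The SES-SFV will also be administered at follow-up to assess for sexual victimization over the interim". Table 1 lists "SES-SFV+MST screener" at both follow-ups but gives its purpose as screening. The Data Analysis section never mentions it. Follow-up reports of sexual trauma are used for referral only.

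**The concern.** Entry and outcome do not cover the same abuse. A woman can qualify through any partner's abuse in the past year, yet on the description given her outcome looks only at her current partner. If she separates and the former partner then abuses her, she has no current-partner abuse to report. Following the stated coding, she moves from IPV-positive to IPV-negative while still being abused.

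Separation is at least a plausible consequence of the program. The goal menu in the SHE modules includes "implement x% of a safety plan for IPV; implement complete safety plan", and the safety checklist records "use of strategies that could protect her from IPV in the future (e.g., hiding money and extra clothing"). If SHE led more women to leave, more abuse would be hidden in the SHE arm, and the IPV component, the risk count and the resolution classes would all lean toward SHE. If separation were equal by arm, there would be no false effect, but the IPV component would lose absolute difference and power. The Power Analysis section makes an effect size for the next trial the main objective, so either distortion would carry forward.

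**Working it through.** **Inputs.** From the Power Analysis section: IPV 25% control versus 8.5% SHE, h = .46, power .80; PTSD 60% and alcohol 40% in control; 126 of at most 155 retained, so 63 per arm if allocation is 1:1. Alpha is .05, sidedness not stated. The share *s* of abused women whose only abuser in the interval is a former partner is **not in the documents**; the values below are assumptions. CAS = 0 is assumed when there is no current partner.

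**1. The plan's own figure.** h = 2·asin(√.25) − 2·asin(√.085) = .456, which matches .46. Power = Φ(h·√(63/2) − z). One-sided: .82 (.80 with pooled proportions). Two-sided: .72 (.70 with pooled proportions). The stated .80 is reproduced at 126 women only as a one-sided test; two-sided figures are used below.

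**2. Unequal hidden shares, no true effect.** Visible rate = T(1 − s), with T = .25 in both arms.

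| s control / SHE | Visible control | Visible SHE | False difference | Hidden women per arm, 63 × .25 × s |
|---|---|---|---|---|
| .10 / .30 | 22.5% | 17.5% | 5.0 points | 1.6 vs 4.7 |
| .20 / .50 | 20.0% | 12.5% | 7.5 points | 3.2 vs 7.9 |

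The false difference is T × (s in SHE − s in control): 3.0 and 4.5 points at T = .15; 7.0 and 10.5 points at T = .35.

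**3. The same error on the primary count.** With PTSD and alcohol contributing .60 + .40 = 1.00 in each arm:
- .10 / .30: 1.175 / 1.225 = .96
- .20 / .50: 1.125 / 1.200 = .94

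**4. Against sampling error.** Treat the three risks as independent at a single visit. For .10 / .30 the variance of the count is .24 + .24 + .225 × .775 = .654 in control and .48 + .175 × .825 = .624 in SHE. SE of the log rate ratio = √[.654 / (63 × 1.225²) + .624 / (63 × 1.175²)] = .12. The false effect is |ln(1.175/1.225)| / .12, about .35 of one standard error. The same steps for .20 / .50 give about .54. Positive correlation among the risks would enlarge the standard error. A second visit would shrink it by at most √2 if the visits were uncorrelated, giving .50 and .76.

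**5. Equal hidden share, planned true effect, s = .20.** 25% versus 8.5% becomes 20% versus 6.8%.
- Absolute difference: 16.5 to 13.2 points.
- Risk ratio: .085/.25 = .34 and .068/.20 = .34, unchanged.
- h: .456 to .400; two-sided power: .72 to .61 (one-sided .82 to .73).

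**6. What the SES-SFV could recover.** If half the hidden events were SES-SFV positive (assumed), adding them back would halve the false differences in step 2, to 2.5 and 3.75 points.

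**The case against.** **The administered wording is not visible.** The document lists a study-measures appendix that is not in the available text. It may hold the actual CAS stem, a partner definition or a rule for unpartnered women. The phrase about the current partner could also mean the partner identified at baseline and followed thereafter. This stands as a limit: the point rests on the description in the Measures section.

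**A reader might infer that a woman sexually assaulted by a former partner during follow-up is definitely scored as having resolved IPV.** The documents do not support that. She must have counted as IPV-positive at baseline, and Aim 4a does not say whether that status comes from the WAST or the CAS. She must have no abusive current partner. And her CAS must be scored 0 rather than left missing.

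**A reader might infer that the primary result is biased toward SHE.** The direction needs differential separation, for which there is no source. The IPV goals listed for SHE are resources, support and safety planning; leaving a partner is not among them. The modules run about 30 minutes each and follow-up is 4 months. Even under the assumed shares, the effect on the count is well under one standard error.

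**A reader might infer that leaving the SES-SFV out of the analysis is itself the defect.** Sexual trauma is not one of the three risks, so its absence from the count follows the design. Without a perpetrator item, using it would count assaults by non-partners as IPV.

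**Dilution depends on the scale.** With equal hidden shares the component risk ratio does not move, and the odds ratio moves only from .28 to .29. The loss is in absolute difference and power.

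None of this removes the mismatch between an entry screen with no stated partner limit and an outcome measure that has one.

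**Conclusion.** The point holds as a defect of outcome scope. On the available text, former-partner abuse during follow-up is not counted in the IPV risk. A woman who was IPV-positive at baseline, has separated and is abused only by the former partner may be scored negative or missing, and may be classed as resolving IPV.

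The size is uncertain and probably modest for the primary outcome. Under the assumed shares the IPV component would show a false benefit of 5.0 to 7.5 points at a true 25% in both arms, but the count would show a false rate ratio of only about .96 to .94. With equal 20% shares there is no false effect; the cost is 3.3 points of absolute difference and two-sided power of about .61 instead of .72 on the IPV component. These figures assume 63 women per arm, a CAS score of 0 when there is no current partner, and hidden shares that the documents do not supply.

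It should be corrected because the remedy is cheap and the trial exists to supply an effect size for a larger one. The safety provisions (DSMB review, referral at follow-up) protect the women but do not change the score. Confidence is medium, chiefly because the measures appendix could not be checked.

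**What to change.** **Main change.** At baseline and at both follow-ups, administer the CAS about any current or former partner. Score the IPV risk on that version at every time point, and score a woman with no partner contact in the interval as 0, not missing. If the appendix already does this, bring the Measures text into line with it.

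**Optional.** Add one follow-up SES-SFV item on the perpetrator (current partner, former partner, other). Repeat the count model and the three-way classification once, with IPV also positive when the SES-SFV records an assault by a current or former partner, and report how many women per arm change class. If data are already collected without that item, treat any positive SES-SFV as an upper bound for the sexual part only, and label it so.

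**Cost.** One changed stem and one scoring rule; if the option is taken, one extra item and one repeat of the planned GEE. CAS scores become less comparable with current-partner use, assessment is slightly longer in a battery meant to be kept short, and the SES-SFV recovers only sexual abuse.
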